NCT02637895
Unique Protocol ID 20150534

Evaluation of the Efficacy of Vortioxetine for Posttraumatic Stress Disorder

Miami PIs: [name].

Miami Co-Investigators: [name], [name]

Emory Sub-Investigators: [name]., [name], [name], Ph.D.; [name].

Version 8, January 22, 2019

I. PROJECT ABSTRACT

Posttraumatic stress disorder (PTSD) is a chronic and common anxiety disorder that follows exposure to an overwhelming traumatic event. The majority of patients with PTSD also meet criteria for other psychiatric disorders and many attempt suicide. Despite its impact on society, little is known about the etiology or pathophysiology of this disorder. PTSD is responsive to pharmacological treatments such as selective serotonin reuptake inhibitors (SSRIs), but response rates rarely exceed 60%, and even fewer patients (20-30%) achieve clinical remission. Thus, there is a clear need to develop novel and improved therapeutics for PTSD.

We will assess the efficacy of vortioxetine using a 12-week, double-blind, parallel-group, placebo-controlled trial of adults with PTSD. Although Vortioxetine has not been approved by the Food and Drug Administration for the treatment of PTSD, it has been approved for the treatment of major depressive disorder and its safety profile is well characterized. In addition to measures of symptomatic improvement in PTSD, we will also assess changes in cognitive function and quality of life. Furthermore, we propose to investigate longitudinally whether certain biological surrogate markers (neurophysiology, genotyping, mRNA) are predictive of treatment response.

II. SPECIFIC AIMS

1. Specific Aim 1 (Primary Aim): To determine the efficacy of Vortioxetine compared with placebo in improving PTSD symptoms.

Hypothesis: PTSD patients randomized to acute therapy (12 weeks) with Vortioxetine will show more improvement in PTSD symptoms compared to patients randomized to placebo, as determined by mean changes in the Clinician-Administered PTSD scale (CAPS-5) score over the course of 12 weeks.

2. Specific Aim 2 (Secondary Aim): To determine the efficacy of Vortioxetine in treating PTSD in terms of overall response rate.

Hypothesis: PTSD patients randomized to acute therapy (12 weeks) with Vortioxetine will have a greater rate of treatment response compared to subjects randomized to placebo, as determined by at least 30% improvement from baseline in CAPS-5 total score and a Clinical Global Impression of Improvement (CGI-I) score of 1 or 2.

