Progress in treating PTSD will also require better understanding of the biological characteristics associated with improvement during treatment. As detailed below, this proposal will use state-of-the-art biological and psychological phenotype measurements to identify moderators and mediators of outcomes with vortioxetine treatment. Through this proposal we are seeking to enhance treatment approaches for PTSD by evaluating the novel compound, vortioxetine, and to apply biological signatures to identify treatment prediction and response. The combined expertise across these sites makes for a unique and complementary research approach. We are not aware of any other research team using these state-of-the-art biological approaches along with expertise in prospective treatment prediction to address these seminal questions in PTSD.

IV. DRUG INFORMATION

A. Investigational Drug: Vortioxetine

Vortioxetine is a newly approved antidepressant with a unique pharmacological profile. It is a potent SSRI and, in addition, has a high affinity for the 5HT_{1D}, 5HT₃, and 5HT₇ receptors where it acts as an antagonist. It is also a 5HT_{1A} agonist and 5HT_{1B} partial agonist. Of particular interest to this PTSD study is the finding that vortioxetine exhibits considerable positive effects on attention, memory, and executive function in patients with major depression, as well as improving performance-based measures of disability.

V. RESEARCH DESIGN AND METHODS

A. Overview of Study

The study design is a 2-site, 12-week, randomized, double-blind, placebo-controlled, parallel-arm, flexible dose trial evaluating the efficacy, safety, and tolerability of Vortioxetine for male and female adult outpatients with PTSD. The primary outcome assessment will occur at 12 weeks. A total of 60 patients will be randomized across the 2 study sites. Subjects must have PTSD symptoms for at least 3 months prior to randomization, and have at least moderate PTSD symptom severity as measured by a score ≥ 28 on the CAPS-5 Past-month version at the screening and baseline visits for inclusion in the study. The study population will be comprised of men and women with PTSD resulting from any form of DSM-5-defined trauma. Combat-related PTSD will not be an exclusion, but no cases with pending litigation or disability claims associated with PTSD will be enrolled.

The 4 study phases consist of the following:

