3) Study period II Treatment (Day 0 to 84): Visits 2 through 9. This is the 12-week period of double-blind placebo-controlled acute treatment. At day 0, EKG for safety monitoring will be conducted. The baseline mRNA sample will be collected. All subjects who continue to meet eligibility criteria will be randomized to one of two groups: Vortioxetine or placebo. Randomization will be performed at a 1:1 ratio into two treatment groups, and both vortioxetine and placebo will be distributed to the patient in blister packs. If a participant is taking 10mg of vortioxetine they will be provided with 2 blister packs at each visit. If a participant is taking 20mg, they will be provided with 4 blister packs. Surrogate marker testing for psychophysiology, mRNA, and neuropsychological testing will be repeated at the completion of the double-blind treatment. Due to the amount of study procedures for certain study visits, we will allow study visits to be done over two days.

4) Follow-Up (Day 84 to 98): Visit 10. Patients will return to the clinic two weeks after the last dose of study medication for assessment of psychiatric status, suicidality, follow-up of any abnormal laboratory or EKG results, and to assist with transition of psychiatric care, if indicated.

See the **Schedule of Events** chart at the end of this section for details of the procedures performed during each visit.

B. Justification of Sample Size

Power Analysis:

Samples of n=60 (2 groups) are associated with reduced but adequate power. Between group differences in change scores of $d=.70$ are detectable with .80 power at $p<.05$. Correlations of

.33 between two variables are detectable with power=.80 in the full sample of 60. Within treatment conditions (n=30) correlations of $r=.50$ are detectable with the same level of power.

C. Informed Consent, Regulatory and Ethical Considerations

The study will be conducted in accordance with Good Clinical Practices (GCP), 21CFR Parts 50 and 56 and all applicable regulatory requirements. Approval for conduct of the study will be obtained from the institutional review boards at both sites.

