Suicidal ideation is assessed at each study visit with the Columbia Suicide Severity Rating Scale (CSSRS), an instrument endorsed by the FDA for clinical trials. This brief instrument systematically tracks suicidal ideation and behavior (e.g., suicide attempts, wish to die, thoughts of suicide, and plan and intent), and classifies events according to the following categories: **Suicidal events** – *completed suicide, suicide attempt, preparatory acts toward imminent suicidal behavior and suicidal ideation.* **Non-suicidal events** – *self-injurious behavior, no suicidal intent and other, no deliberate self-harm.* **Indeterminate or potentially suicidal events** – *self-injurious behavior, suicidal intent unknown.* Subjects who are considered by the study psychiatrist to be at high risk for suicide are discontinued from the study and referred for hospitalization and further treatment as clinically indicated.

Poor Adherence: Every effort will be made to encourage subject compliance with the dosage regimen as per the protocol. A record of the supplies dispensed, taken and returned will be recorded at each visit. Compliance will be monitored by pill counts. Subjects who miss three or more consecutive days of Vortioxetine during the study are considered non-compliant and will be counseled about need for adherence. Patients found to miss three consecutive doses of study medication twice will be withdrawn from the study. Non-adherent patients are classified as dropouts in the analysis.

Drop-outs: Drop-outs will be defined as randomized subjects lost to follow-up who do not complete the 12-week double-blind treatment period. Randomized subjects who drop out prior to completing one post-randomization efficacy assessment will not be included in the primary efficacy analysis.

SCHEDULE OF EVENTS											
Visit Number	S1	V1	V2	V3	V4	V5	V6	V7	V8	V9	V10
Week (± 2 days for V2-V4, ± 3 days for V5-10)		-1	0	1	2	4	6	8	10	12	14
Day		-7	0	7	14	28	42	56	70	84	98
Informed consent	X										
Demographics/Hollingshead	X										
Vital signs	X	X	X	X	X	X	X	X	X	X	X
Weight	X		X			X		X		X	X
Psych/Medical eval. by MD	X									X	
Physical examination	X									X	
12-lead EKG	X		X							X	
MINI modules A, C-P	X										
Dispense Study Drug & Diary			X	X	X	X	X	X	X		
Laboratory Tests											
CBC	X									X	
Blood Chemistry	X									X	
Liver Function Tests	X									X	
GGT	X										
Urinalysis	X									X	
Urine drug screen	X										
Serum Pregnancy	X									X	

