Multiple outcome measures: To address the possible increase in Type I errors due to multiple outcome variables, we have a priori selected a single outcome measure (CAPS total) which will maintain the significance level (α) 0.05 for the primary analysis. For secondary outcome measures, we will adjust p-values by controlling for the false discovery rate (Benjamini & Hochberg, 1995) and report both unadjusted and adjusted p-values.

Random effects: Given that the majority of outcomes are behavioral in nature, we expect that there will be significant individual level variance that will need to be incorporated into the model. Thus our overall analysis approach will be to use linear 2-level mixed models or generalized linear mixed models, as appropriate, to analyze the repeated measures data with at least a random intercept to incorporate individual level variation. We will also incorporate a random slope if necessary however, it is not always necessary in our experience, particularly with scales with a limited range such as MADRS.

VIII. HUMAN SUBJECTS

Updated January 22, 2019

A. Subject Recruitment

Men and women between the ages of 18-65 with a primary diagnosis of PTSD using the DSM-V criteria will be eligible for the study. A total of 60 subjects will be randomized (30 to Vortioxetine and 30 to placebo). These subjects will be enrolled at 2 sites, Emory University School of Medicine and Miami Miller School of Medicine. Subjects will enter this study having been recruited through referrals from outpatient clinics, or referrals from other community clinics and community clinicians (psychiatrists, psychologists, and social workers) in the greater Atlanta and Miami regions. In addition, we will advertise locally in newspapers and radio and will post recruitment messages on internet sites.

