Subjects will meet all inclusion/exclusion criteria outlined below. We will exclude subjects with history of bipolar disorder, psychosis, substance abuse or dependence that is current or existed 3 months prior to screening, history of borderline intellectual functioning or mental retardation, and clinically significant suicidal risk. We will exclude individuals with the following medical conditions, as evidenced by use of daily medications or prior treatment: cancer in past year, stroke, heart attack, angina, neurological disease (MS, epilepsy, Parkinson's), CNS lesions (head trauma), dementing illness, liver/kidney disease. The completion of self-report scales and cognitive tests requires a level of understanding that may not be present in those with low IQ. Medical illnesses and use of medication that may interfere with biological, and possibly psychological assessments, and current suicidality that requires immediate clinical intervention will be exclusionary for participation.

B. Inclusion/ Exclusion Criteria

Inclusion

CRITERION	METHOD OF ASCERTAINMENT
1. Males and Females between the ages of 18 and 65	History
2. Fulfills DSM-5 criteria for primary diagnosis of PTSD.	MINI
3. Willing and able to give consent	Clinical interview
4. A negative urine toxicology	Urine toxicology
5. For females of reproductive age, use of an effective birth control method* for the duration of the study or abstinence.	History
6. Duration of illness of PTSD for at least 3 months	History
7. An initial score at Screening, and Visit 2 (randomization) of ≥ 28 on the CAPS-5 for PTSD Studies	CAPS-5

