Appendix B. Description of Scales

Brief Assessment of Cognition in Schizophrenia (BACS)

The Brief Assessment of Cognition in Schizophrenia (BACS) is a clinician-rated instrument that measures cognitive function. The domains of cognitive function that are assessed by the BACS include verbal memory, working memory, motor speed, attention, executive functions and verbal fluency. It is designed to require about 30 min of testing time. BACS A will be performed at V1 and Version B will be performed at V9.

UCSD Performance-Based Skills Assessment- Brief Version (UPSA-B)

The UCSD Performance-Based Skills Assessment (UPSA-Brief) is a role-play test designed to evaluate a person's functional capacity in two selected areas of basic living skills. The UPSA-Brief (UPSA-B) was developed as an abbreviated alternative to the full version of the UPSA ([Mausbach et al., 2007](#)) and contains 2 of the original 5 subscales of the full UPSA (i.e., finance and communications subscales), which allows for shorter administration time (10–15 minutes) and reduced reliance on testing props. An UPSA-Brief Total Score (range = 0–100) is then obtained by summing the subscale scores.

Clinical Global Impressions Improvement Scale (CGI-I) and Severity Scale (CGI-S)

The CGI-I (Guy 1976) is a clinician-rated instrument that measures the degree of the patient's improvement. It is a 7-point scale where 1 = very much improved; 4 = no change; and 7 = very much worse. Baseline for assessing improvement for the CGI-I ratings will be the patient's clinical status at Visit 3. The CGI-S is a similar clinician-rated instrument that measures the overall severity of the patient's illness as compared to the overall study population. It is also a 7-point scale where 1 = normal, not at all ill; 4 = moderately ill; and 7 = among the most extremely ill patients.

Clinician-Administered PTSD Scale (CAPS-5)

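### Appendix B anchors the CGI-I to Visit 3, a week into double-blind treatment, so the two halves of the Aim 2 response definition use different baselines

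*Combined protocol and SAP*

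**What the plan says.** Specific Aim 2 defines treatment response by two conditions that must both hold: "at least 30% improvement from baseline in CAPS-5 total score and a Clinical Global Impression of Improvement (CGI-I) score of 1 or 2".

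Appendix B, in the entry for the CGI scales, fixes the reference point for the second condition: "Baseline for assessing improvement for the CGI-I ratings will be the patient's clinical status at Visit 3". No other section gives a CGI-I anchor.

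The reference point for the first condition has to be inferred. Section V.A requires a qualifying score on the "CAPS-5 Past-month version at the screening and baseline visits for inclusion in the study". Inclusion criterion 7 in Section VIII.B states the same requirement with visit names, beginning "An initial score at Screening, and Visit 2 (randomization". Read together, they make Visit 2 the baseline visit.

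Section V.A describes Study Period II as "Visits 2 through 9. This is the 12-week period of double-blind placebo-controlled acute treatment". In the Schedule of Events, the row "Dispense Study Drug & Diary" has its first mark at Visit 2.

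**The concern.** A baseline for rating improvement should come before treatment starts and should be the same for both parts of a composite. Here the CGI-I reference is a visit at which patients have already had about a week of vortioxetine or placebo.

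Three things follow if the text is applied literally.

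- Any first-week change, whatever its cause, is absorbed into the CGI-I reference but still counts towards the CAPS-5 criterion. Early improvement makes a CGI-I of 1 or 2 harder to reach; early worsening makes it easier.
- The anchor comes after randomisation, so it can itself be affected by treatment. If week-1 status differs between arms, the secondary response comparison could be distorted, in either direction.
- A rater who follows Appendix B would use Day 7, and one who follows the layout of the schedule would use Day 0. If the two sites settle this differently, a CGI-I of 2 does not mean the same thing at both. Section VII.B tests all outcomes for site differences and replaces the planned analyses with stratified ones if response differs by site, so an artefact of the anchor could contribute to that switch.

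Any other analysis that reuses this responder status would inherit the problem. The document does not say whether Exploratory Aim 3 does.

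**Working it through.** No figure in the plan needs reproducing. The check sets the anchor against the schedule.

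**Inputs from the Schedule of Events** (columns S1, V1, V2 to V10)

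| Item | Visit 2 | Visit 3 |
|---|---|---|
| Day | 0 | 7 |
| Study drug dispensed | yes (first time) | yes |
| CAPS and CGI | yes | no |
| MADRS | yes | no |
| PCL-5 and QIDS-SR | yes | no |
| PSQI | yes | no |
| SDS | yes | no |
| CSSRS | yes | yes |
| PRISE and concomitant medication | yes | yes |
| FIBSER | no | yes |

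The CAPS and CGI row is marked at S1, V2, V4, V5, V7 and V9 only.

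**Timing.** The schedule header gives the windows: "Week (± 2 days for V2-V4, ± 3 days for V5-10". Visit 3 therefore falls between Day 7 − 2 = 5 and Day 7 + 2 = 9. With Visit 9 at Day 84, the CAPS-5 half spans 84 − 0 = 84 days and the CGI-I half spans 84 − 7 = 77 days at nominal dates.

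**Can both halves share Visit 3?** No. There is no CAPS-5 at Visit 3 from which to calculate a 30% improvement. The only CAPS-5 assessments before treatment are at S1 and V2, and neither is Visit 3. The mismatch therefore does not depend on the inference that Visit 2 is the CAPS-5 baseline.

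**Does Appendix B number visits differently?** No. The BACS entry in the same appendix places the test at V1 and V9, as the schedule does. The pharmacokinetic visits (5, 7 and 9) and the randomisation visit (2) also agree with the schedule. A slip is still plausible, because the randomisation visit is the third column (S1, V1, V2).

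**Illustration of the mechanism (assumed values).** Suppose symptoms fall by a fraction *w* between Visits 2 and 3, and a patient ends exactly 30% below Visit 2. Relative to Visit 3, the improvement is 1 − 0.70/(1 − *w*):

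- *w* = 0%: 30.0%
- *w* = 5%: 26.3%
- *w* = 10%: 22.2%
- *w* = 15%: 17.6%
- *w* = 20%: 12.5%

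The CGI-I is a global judgement and not a percentage, so this shows how the two references diverge; it does not predict ratings.

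**Scale of a reclassification.** A patient's status changes only if the 30% CAPS-5 criterion is met and the choice of anchor moves the CGI-I across the boundary between 2 and 3. With 30 per arm, a net 1, 2 or 3 such patients (assumed range) shifts that arm's response rate by 1/30 = 3.3, 2/30 = 6.7 or 3/30 = 10.0 points.

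**The case against.** The strongest reply is that this is a one-digit slip with no demonstrated effect. The schedule puts the CGI at Day 0 and omits it at Visit 3, so a sensible rater would use Visit 2. The endpoint is secondary and adjusted for the false discovery rate. The point shifts above would apply to any binary endpoint with 30 per arm and say nothing about this anchor in particular.

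There are also safeguards. Recordings are used for interrater reliability training and assessment, the lead coordinator is responsible for uniform procedures, and the investigators review procedures monthly. Randomisation is blocked by site, so a site-specific anchor would apply to both arms within that site.

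Much of this stands. A slip is a likely explanation, no material distortion has been shown, and blocking limits the harm from the sites merely differing. Two points remain. Blocking does not help if status at Day 7 itself differs by arm, since the anchor is measured after randomisation. And none of the safeguards states the right anchor: raters trained uniformly on Appendix B would uniformly use Day 7.

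**Conclusion.** The concern holds. The CGI-I anchor is wrong as written and should be corrected. It is the only stated rule for half of a named secondary endpoint, and it conflicts with every scheduled pre-treatment CAPS-5 assessment.

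Confidence in the conflict between the texts is high. Its effect on the response comparison is unknown in size and direction, because the document gives no week-1 data and no CAPS or CGI is scheduled at Visit 3. The primary analysis is untouched: under multiple outcome measures, Section VII.B says "we have a priori selected a single outcome measure (CAPS total", and that measure does not use the CGI-I.

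**What to change.** In Appendix B, replace Visit 3 with Visit 2 (Day 0, before the first dose). State, in Specific Aim 2 or Section VII.B, that Visit 2 is the baseline for both parts of the response definition. Put the same sentence in the rater instructions at both sites.

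This costs a wording change and a rater note. No visit or assessment is added, because the CGI is already scheduled at Visit 2.

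The document is Version 8 and does not report enrolment status. If CGI-I ratings have already been made, new wording will not re-anchor them. In that case, record before unblinding which anchor raters used at each site; this is the informative step. Add one sensitivity analysis of response on the 30% CAPS-5 criterion alone. That analysis is free of the anchor, but it also drops the CGI-I requirement altogether, so a difference from the composite result could not be attributed to the anchor.
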